9.5. Review and open-label single-arm stage (SA3) (month 12)

At 12 months after randomisation R1, the participant will attend a 6 monthly review with full assessments as per baseline as above, with OCT scan arranged for two weeks prior.

- Participants who received Tirzepatide at R2 will proceed to their final follow up contact (**section 9.6**).
- Participants who did not receive Tirzepatide at R2 will receive 6 months of open-label Tirzepatide and continue with monthly follow up appointments as per **section 9.3**.
- At 18 months a full review as per the baseline visit as detailed in **section 9.2** (minus height, demographics and medical history) will be carried out.

9.6. Follow up (final dose of Tirzepatide + 5 weeks)

Five weeks after their final dose of Tirzepatide (whenever this occurs for each participant), all participants will be invited to attend a short follow up call, where a health and wellbeing check will be carried out as per recommended routine practice when losing weight using Tirzepatide. They will then leave the trial.

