3.1.4. Trial exit at all stages

In all stages, participants who receive Tirzepatide will have a final well-being follow up appointment with the trial researcher 5 weeks after the last dose of the drug, which completes their involvement in the trial.

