Informed consent is defined as the process of learning key facts about a clinical trial before deciding whether or not to participate. It is a continuous and dynamic process and participants should be asked about their ongoing willingness to continue participation at all visits. Participants should be aware from the beginning that they can freely withdraw (cease to participate) from the trial at any time. A participant may wish to cease to participate in a particular aspect of the trial. The changes in levels of participation within the trial are categorised in the following ways:

No trial intervention: The participant would no longer like to receive the trial intervention, but is willing to be followed up in accordance with the schedule of assessments and if applicable using any central UK NHS bodies for long-term outcomes (i.e. the participant has agreed that data can be collected and used in the trial analysis).

No further data collection: The participant is not willing to be followed up in any way for the purposes of the trial AND does not wish for any further data to be collected (i.e. only data collected prior to any changes of levels in participation can be used in the trial analysis).

The details of changes of levels in participation within trial (date, reason and category of status change) will be entered onto the Participant Change of Status Form on the EDC. Participants can change their level of participation without giving a reason.

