12.3. Adverse event reporting in IIH-Advance

The reporting period for adverse events in IIH-Advance will be from the day of randomisation until the end of follow up (i.e. 5 weeks after the last dose, if having taken Tirzepatide). The safety profile for this trial population and rapid weight loss regimens are well characterised so a strategy of targeted reporting of adverse events will not affect the safety of participants: only Serious Adverse Events (SAEs) will be reported.

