16.1. Sample size

Examination of various IIH datasets held (including the IIH:WT trial²⁵, the IIH:Life cohort, and our previously published clinical trials in IIH²⁶) suggest it is anticipated that in the population of patients who receive standard of care only 5% will have resolution of papilloedema (100% reduction in the excess elevation of the optic nerve swelling). Further analysis of these datasets revealed that in those who achieved at least a 12% reduction in body weight, between 30 and 50% had a complete resolution of papilloedema. For the purposes of the sample size calculation, we have taken a conservative estimate of 37% (the median estimate).

With a type I error of 0.05, a type II error of 0.1 (corresponding to a power of 90%), a responder rate in the control arm of 5% and responder rate of 37% in the Tirzepatide arm, a sample size of 32 participants per arm is required. Inflating this to account for 25% attrition (for missing data and withdrawal) would require 43 patients per arm (86 overall).

After 50% of the planned sample size has been recruited and treated (i.e. at the end of the first randomisation R1), an assessment of the missing data is planned to ensure the levels observed fall below that assumed during this calculation, with the option to increase the sample size based on this if needed. This trial has been powered to answer the primary question for R1 only. The subsequent questions remain unpowered. This remains a limitation, however powering for these questions would result in a trial sample size that was infeasible. The purpose of these questions is to provide some high-quality evidence.

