16.2. Analysis of outcomes

A separate Statistical Analysis Plan will be produced and will provide a more comprehensive description of the planned statistical analyses. A brief outline of the planned analyses is given below.

Unless reported otherwise, the threshold for determining statistical significance from hypothesis testing will be represented by a p-value of <0.05. Where parametric tests have been specified dependent on the normality of data distribution, this will be assessed using appropriate graphics (for example histograms and q-q plots) prior to application of the test. Where randomisation is minimised by stratification variables, the main estimators will be adjusted for such variables for the primary outcome at stage R1.

Data pertaining to outcome measures will be transformed as per user manuals and standard practice to derive clinically meaningful indices where relevant.

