16.2.1. Primary outcome

Resolution of papilloedema at the 6 month assessment. Where patients are missing the primary outcome (for example due to non-attendance at 6-month visit), they shall be treated as a failure and included in the denominator only (unless there is data from an unscheduled visits which could be utilised).

Resolution of papilloedema will be reported as n/N where n is the number of participants with resolution of papilloedema and N the total number of participants in the corresponding trial arm, and percentages as appropriate. Logistic regression model will be used to analyse the primary outcome. Risk ratio, risk difference and the associated 95% confidence intervals will then be derived using marginal standardisation method.

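### The exit rule tied to the last Tirzepatide dose conflicts with section 11 and, followed as written, loses the month-6 OCT of early stoppers in one arm only

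*Protocol*

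**What the plan says.** **Exit.** Section 9.6 sets the closing contact by the last dose: "Five weeks after their final dose of Tirzepatide (whenever this occurs for each participant), all participants will be invited to attend" a short health and wellbeing call. It ends: "They will then leave the trial". Section 3.1.4, which covers exit at all stages, places the final appointment "5 weeks after the last dose of the drug, which completes their involvement in the trial". Table 1 lists a safety check and a fit-and-well check at that contact, and no OCT.

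**Stopping treatment.** Section 11 defines a level of participation for someone who no longer wants the intervention but is "willing to be followed up in accordance with the schedule of assessments". Table 1 puts an OCT at month 6, and section 9.4 asks for it in the two weeks before that time point.

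**Missing primary outcome.** Under section 16.2.1, participants without a month-6 result are handled as follows: "they shall be treated as a failure and included in the denominator only". The one exception is usable data from an unscheduled visit.

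**Safety reporting.** Section 12.3 runs adverse event reporting from randomisation "until the end of follow up (i.e. 5 weeks after the last dose, if having taken Tirzepatide").

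**The concern.** A participant who stops Tirzepatide at month 2 cannot both leave at about month 3 and attend at month 6. Section 11 points to the second course, sections 3.1.4 and 9.6 to the first, and no text ranks them.

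Section 11 also leaves some stops uncovered. It is worded for a participant who chooses to give up the intervention. Stops directed by the protocol, such as on pregnancy (7.2.3) or when Tirzepatide is halted on an urgent referral for visual deterioration (9.7), are not literally within it. For those, 9.6 is the only exit text.

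What is at stake is the primary comparison. During R1 only the Tirzepatide arm has a last dose, so only that arm can meet the exit trigger. Missing outcomes would then arise from treatment discontinuation in one arm and be turned into failures. The estimate would move away from the effect of being allocated to Tirzepatide whether or not it is continued. The protocol expects some tolerability problems (7.3) and makes all-cause discontinuation an outcome (8.1.2), so the case is not hypothetical.

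**Working it through.** **Timing.** A month is 28 days (7.1), so month 6 is week 24 and the OCT falls in about weeks 22 to 24. Exit is at last dose + 5 weeks. Exit comes before the scan window opens if last dose + 5 < 22, that is, if the last dose is before about week 17. From week 17 to 19 (24 − 5) the order depends on the dates. After week 19 the scan comes first. These limits ignore the ±7-day visit windows.

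**The plan's own figure.** Inputs from 16.1: 5% v 37%, type I error 0.05, power 90%, 25% attrition. Sidedness is not stated there, and 16.2 says only that "the threshold for determining statistical significance from hypothesis testing will be represented by a p-value of <0.05". I assume a two-sided test with pooled variance and no continuity correction:

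n = [1.960·√(2p̄(1−p̄)) + 1.2816·√(p1(1−p1) + p2(1−p2))]² / (p2−p1)², with p̄ = 0.21

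= [1.1290 + 0.6789]² / 0.1024 = 31.9, so 32 per arm. Then 32/0.75 = 42.7, so 43 per arm and 86 in all. Both figures reproduce.

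**Power with every month-6 OCT obtained.** At 43 per arm: z = (0.32·√43 − 1.1290)/0.5297 = (2.0984 − 1.1290)/0.5297 = 1.830, power 96.6%.

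**Power if early stoppers leave and count as failures.** Let s be the share of the Tirzepatide arm whose last dose is early enough to miss the scan, and r the rate at which they would have shown resolution if scanned. Take 37% as the rate over the whole arm. The scored rate is 0.37 − s·r; the control rate stays at 5%. The documents give neither s nor r. I assume s = 5 to 15%, with r from 5% (the control rate) to 37% (the upper bound).

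| s | Scored rate, r = 37% | Power | Scored rate, r = 5% | Power |
|---|---|---|---|---|
| 5% | 35.2% | 95.1% | 36.8% | 96.5% |
| 10% | 33.3% | 93.0% | 36.5% | 96.3% |
| 15% | 31.5% | 90.2% | 36.3% | 96.1% |

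Example, s = 10% and r = 37%: scored rate 0.37 − 0.037 = 0.333; z = (0.283·√43 − 1.0907)/0.5192 = 1.473, power 93.0%.

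The risk difference shrinks by s·r: at worst 1.9, 3.7 and 5.6 percentage points, and at r = 5% by 0.25, 0.5 and 0.75 points. In people, the upper bound at s = 10% is 43 × 0.10 × 0.37 = 1.6 resolutions scored as failures. Outside the assumed range, s = 20% with r = 37% would give 86.8%.

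**Safety window.** Someone re-randomised at month 6 to stop Tirzepatide (R2b) who then receives it in SA3 takes a last dose near month 18. The 12.3 window, read to that dose, spans the whole withdrawal stage. Someone in R2b who does not go on to SA3 took the last dose near month 6, and the window closes about five weeks into that stage. Section 3.1.3 describes SA3 as an offer, so such participants are possible.

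**The case against.** The strongest reply is that the literal reading is not the design. Sections 9.4 and 9.5 send participants to 9.6 only after the month-6 or month-12 scan and review, so the phrase about timing most naturally covers planned ends of treatment at months 6, 12 and 18. Read literally, the rule would also discharge every R2b participant five weeks into R2, although 3.1.2 and 9.5 plan their month-12 assessment. Voluntary early stopping has its own, more specific rule in section 11. This stands as evidence of intent: removal of early stoppers is what 3.1.4 and 9.6 say on their face, not a certain outcome. It does not remove the conflict, because neither section limits itself to planned ends and protocol-directed stops fall outside section 11's wording.

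Two stronger readings are tempting.

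- A reader might infer that SAE capture is lost for about 19 of the 24 weeks (24 − 5) of the withdrawal stage for everyone in R2b. The documents do not support this. Those who go on to SA3 have a later last dose, and Table 1 schedules safety checks in months 7 to 12 regardless.
- A reader might add early stoppers to the planned 25% attrition, score both as failures, and arrive at power of 84.7, 81.3 and 77.3% for 5, 10 and 15% stopping. Section 16.1 says the 25% already covers missing data and withdrawal, so this counts some participants twice. Its starting point of 87.7% (27.75% v 3.75%) comes from scoring all attrition as failure in both arms, which is a separate question.

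It is also fair that r = 37% is a ceiling. In 16.1 that rate belongs to people who lost at least 12% of body weight, which someone stopping in the first months is unlikely to have done.

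**Conclusion.** The contradiction is real. Sections 3.1.4 and 9.6 end participation by the last dose without exception, and section 11 does not. Followed as written, the exit rule loses the primary scan for Tirzepatide participants whose last dose is before about week 17, and the failure rule turns that loss into a bias towards no difference. The failure rule itself applies to both arms; only the exit trigger is one-sided. The bias does not favour Tirzepatide, and unscheduled scans may rescue some participants.

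Under the assumed 5 to 15% stopping, power stays at or above 90% even at the upper bound and hardly moves if stoppers resolve at 5%. These figures take all other month-6 outcomes as observed. A loss of the planned power is therefore not shown. The case for correction is that the text gives two instructions for the primary outcome and that a missed month-6 scan cannot be recovered later. Within the withdrawal stage, the wording of 12.3 leaves a reporting gap only for R2b participants who do not receive Tirzepatide in SA3.

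**What to change.** Reconcile 3.1.4, 9.6 and 12.3 with section 11 by stating three things:

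1. Stopping Tirzepatide, for any reason, does not end participation.
2. Participants who have not withdrawn from data collection keep their scheduled assessments, including the month-6 OCT.
3. Trial exit and the end of SAE reporting are the later of five weeks after the last dose and the last scheduled assessment of the participant's final stage.

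This concerns data collection only and takes no view on when treatment should stop. The cost is a few sentences in an amendment. The visits and scans are already in the schedule, and the sample size does not change.

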9.7. Unscheduled OCT visits

If there is deterioration (or suspected deterioration) of visual function, additional OCT visits should be scheduled with Specsavers to ensure the participant's ongoing visual health, as would be recommended in routine NHS practice. If required, an urgent referral to the NHS will be arranged and Tirzepatide halted.

10. Schedule of assessments

Table 1: Schedule of Assessments (Researcher completed)

Visit	0	1	R1				R2		SA3		Follow up 5 weeks after stopping intervention
	Screening	Baseline/ Randomisation	2-3 Months 1-2	4 Month 3	5-6 Months 4-5	7 Month 6	8-12 Months 7-11	13 Month 12	14-18 Months 13-17	19 Month 18	
Visit window (days)	(-14)	(+14)	(+/-7)	(+/-7)	(+/-7)	(+/-7)	(+/-7)	(+/-7)	(+/-7)	(+/-7)	(+/-7)
Eligibility check		x				x		x			
Valid informed consent	x										
OCT Imaging	x					x		x		x	
Ophthalmic review		x				x		x		x	
Medical, IIH and ophthalmic history*		x									
Concomitant medication		x	x	x	x	x	x	x	x	x	
Demographics		x									
Randomisation		x				x					
Height	x										
Weight and BMI	x	x	x	x	x	x	x	x	x	x	
Urine pregnancy test		x				x		x			
Safety and adverse events check			x	x	x	x	x	x	x	x	x
Fit and well check											x
Trial medication training		x				x		x			
Trial medication dispensing		x	x	x	x	x	x	x	x	x	
Trial medication adherence			x	x	x	x	x	x	x	x	

*assessed by Trial Doctor

NB: OCT imaging performed at local participating Specsavers UK store

Table 2: Schedule of Assessments (Participant completed)

Visit	0	1	2-3	4	5-6	7	R1		R2		SA3	
	Screening	Baseline/ Randomisation	Months 1-2	Month 3	Months 4-5	Month 6	Months 7-11	Month 12	Months 13-17	Month 18	14-18	19
Visit window (days)	(-14)	(+14)	(+/-7)	(+/-7)	(+/-7)	(+/-7)	(+/-7)	(+/-7)	(+/-7)	(+/-7)	(+/-7)	(+/-7)
CSRI		x	x	x	x	x	x	x	x	x	x	x
Headache Diary		x	x	x	x	x	x	x	x	x	x	x
HIT-6 questionnaire		x	x	x	x	x	x	x	x	x	x	x
WPAI		x				x		x				x
SF-36		x				x		x				x
EQ5D-5L		x				x		x				x
NEVI VFQ-25		x				x		x				x
Binge Eating Questionnaire		x				x		x				x
AUDIT		x				x		x				x
HADS		x				x		x				x
PSQI		x				x		x				x
ISI		x		x		x						
Berlin Questionnaire		x		x		x						
STOP-Bang		x		x		x						
Research biological sample collection		x		x		x		x			x	
Sleep / activity tracker (2 weeks prior)		x		x		x						

11. Withdrawal and changes in levels of participation

Informed consent is defined as the process of learning key facts about a clinical trial before deciding whether or not to participate. It is a continuous and dynamic process and participants should be asked about their ongoing willingness to continue participation at all visits. Participants should be aware from the beginning that they can freely withdraw (cease to participate) from the trial at any time. A participant may wish to cease to participate in a particular aspect of the trial. The changes in levels of participation within the trial are categorised in the following ways:

No trial intervention: The participant would no longer like to receive the trial intervention, but is willing to be followed up in accordance with the schedule of assessments and if applicable using any central UK NHS bodies for long-term outcomes (i.e. the participant has agreed that data can be collected and used in the trial analysis).

No further data collection: The participant is not willing to be followed up in any way for the purposes of the trial AND does not wish for any further data to be collected (i.e. only data collected prior to any changes of levels in participation can be used in the trial analysis).

The details of changes of levels in participation within trial (date, reason and category of status change) will be entered onto the Participant Change of Status Form on the EDC. Participants can change their level of participation without giving a reason.

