9.4. Review and treatment allocation visit R2 (month 6)

With sufficient notice before the 6 month time point, an OCT scan will be arranged at a participating Specsavers UK store of the participant's choice, to be completed <2 weeks before the 6 month time point.

Then, at 6 months, a full review as per the baseline visit as detailed in **section 9.2** (minus height, demographics and medical history) will be carried out.

Once the OCT scan has been analysed by the trial researcher and all month 6 assessments have been completed, participants will be classed as responder, partial responder or non-responder.

- Responders to standard of care will leave the trial.
- Non-responders to Tirzepatide will proceed to their final follow up visit (**section 9.6**).
- Responders and partial responders to Tirzepatide, and partial and non-responders to standard of care will be re-randomised into R2 as per the R1 randomisation method in **section 6**.

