12.2. Adverse event recording – general

The recording and reporting of adverse events will be in accordance with the UK Policy Framework for Health and Social Care Research and the requirements of the Health Research Authority (HRA). Definitions for adverse event reporting are listed in **Table 3: Adverse Event reporting definitions in section 12.1**.

It is routine practice in NHS research to record adverse events in the participant's medical notes and it is also recommended that this includes the documentation of the assessment of severity and seriousness and of causality (relatedness) in relation to the intervention in accordance with the protocol. We will therefore mirror what would be expected in an NHS participant's notes; a notes field will be created on the eCRF for each follow up assessment to serve the function of medical notes. The trial researcher will review all potential AEs with participants at each appointment and record the discussions, including an evaluation of these events.

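### The ±7-day window on the closing safety call lets participants leave up to a week before the 5-week SAE reporting period ends

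*Protocol*

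**What the plan says.** Section 12.3 limits reporting to serious events and sets the period as running "from the day of randomisation until the end of follow up (i.e. 5 weeks after the last dose, if having taken Tirzepatide".

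Section 9.6 places a short closing call five weeks after the final dose and adds: "They will then leave the trial". Section 3.1.4 describes the same contact as taking place "5 weeks after the last dose of the drug, which completes their involvement in the trial".

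Table 1 in section 10 labels this contact "Follow up 5 weeks after stopping intervention", schedules a safety and adverse event check at it, and gives it a window of ±7 days.

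On how events come to light, section 12.2 says: "The trial researcher will review all potential AEs with participants at each appointment".

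Three groups reach this closing contact straight after a course of Tirzepatide:
- those without a response at month 6 (section 9.4: "Non-responders to Tirzepatide will proceed to their final follow up visit");
- those treated in R2 (section 9.5: "Participants who received Tirzepatide at R2 will proceed to their final follow up contact");
- those treated in SA3, through section 9.6.

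**The concern.** A symmetric window does little harm at a visit that is followed by another one, because the next visit asks about the days that an early visit left out. The closing call has no successor. If it is made before day 35, the participant has left the trial while the reporting period in section 12.3 is still open, and nobody is scheduled to ask about the remaining days. The call nevertheless counts as compliant, so monitoring would not flag it.

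What is at stake is the capture of SAEs in the last days of the post-dose period that the protocol chose for itself. After an early call, such an event would be known only if the participant volunteered it. The wording of section 12.3 also leaves staff unsure which date closes reporting for a given participant: the call, or day 35.

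**Working it through.** **Inputs**
- End of the SAE reporting period: 5 weeks after the last dose (section 12.3), i.e. 5 × 7 = 35 days.
- Target day of the closing call: five weeks after the final dose (sections 3.1.4 and 9.6), also day 35.
- Window: the last entry of the window row in Table 1. The row has 11 entries (−14, +14, then nine of ±7) for 11 visit columns, so the last entry, ±7, belongs to the follow-up column.
- Last scheduled safety check: the safety row of Table 1 has its final mark in that same column. No later contact is scheduled.

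**Permitted call days**

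Earliest: 35 − 7 = 28. Latest: 35 + 7 = 42. Number of permitted days: 42 − 28 + 1 = 15.

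**Days of the reporting period left without an enquiry**

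For a call on day d, gap = max(0, 35 − d).

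| Call day | 28 | 29 | 30 | 31 | 32 | 33 | 34 | 35 to 42 |
|---|---|---|---|---|---|---|---|---|
| Gap (days) | 7 | 6 | 5 | 4 | 3 | 2 | 1 | 0 |

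The largest gap is 7 days, or 7/35 = 20% of the period (days 29 to 35).

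**Average, under an assumption**

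The protocol does not say how call dates will be distributed. If they were spread evenly over the 15 permitted days:
- share of early calls: 7/15 = 46.7%;
- mean gap: (7 + 6 + 5 + 4 + 3 + 2 + 1)/15 = 28/15 = 1.87 days;
- as a share of the period: 1.87/35 = 5.3%.

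Without that assumption, the mean gap lies between 0 days (every call on day 35 or later) and 7 days (every call on day 28).

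**Who is affected**

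The gap concerns the three groups that leave after their last dose. It does not concern participants re-randomised from Tirzepatide to standard of care at month 6. The five weeks after their R1 course are covered by the monthly safety checks of months 7 to 11.

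**With a 0/+7 window**

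Permitted days are 35 to 42, i.e. 8 days, and the gap is 0 on each of them.

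**The case against.** The best reply is that section 12.3 ties the period to the end of follow-up, and that its bracket merely gives the nominal time of a visit that carries a tolerance. On that reading, reporting and the last enquiry stop together and there is no gap. It is a possible reading, but section 12.3 itself explains the end of follow-up as 5 weeks after the last dose. If the call date is meant to govern, the stated 5 weeks is wrong for every early call. One of the two places needs correcting either way.

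A second reply is that ±7 days is ordinary tolerance, used at every visit after baseline, and that the instruction is to call at five weeks. Both are true, and calls booked to a day-35 target may well cluster there. The even-spread figures are therefore illustrative, and the only firm number is the 7-day maximum. Ordinary tolerance is still less suitable at the last contact, for the reason given above.

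A third reply is that the reporting duty in section 12.4.3 starts when the team learns of an event, whether or not a call was scheduled. That stands as far as it goes: an SAE volunteered on day 32 could still be reported. But the duty creates no enquiry, and section 12.5.3 follows up only SAEs already reported.

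Finally, no trial conclusion depends on this. The trial is not a CTIMP, section 3.1 says that it does not examine the drug's safety, and SAE rates are not among the listed outcomes. That limits the importance of the point but does not remove the mismatch.

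**Conclusion.** The concern holds. The visit window and the SAE reporting period do not fit together: a compliant closing call can end participation up to 7 days before the period in section 12.3 is over, with no later scheduled contact. This rests on the alignment of Table 1 (11 entries for 11 columns) and on reading 5 weeks in section 12.3 as day 35, as its own wording indicates.

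The size is modest: 0 to 7 days per participant who leaves after a last dose, and 1.9 days on average if call dates are evenly spread. No count of missed SAEs can be derived, because the protocol gives no event rate for these days. The contraception requirement is a separate duty on the participant and is unaffected, as is the primary analysis. This is a cheap improvement to safety capture that should be made; it does not threaten the trial's results.

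**What to change.** Make two small edits:
1. In Table 1, change the window of the final follow-up column from ±7 to 0/+7 days, so that the call falls on days 35 to 42 after the last dose.
2. In section 12.3, state that for participants who have taken Tirzepatide, SAE reporting runs to day 35 after the last dose or to the closing call, whichever is later.

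The cost is one table cell and one clause. No visit is added. The only drawback is a tighter booking range for one remote call, 8 permitted days instead of 15.
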